### Measures taken the morning of psilocybin session prior to drug administration (for psilocybin condition only):

*Pre-Session Questionnaire:* To assess the psychological "set" of the volunteer before the session, subjects will complete a brief questionnaire before psilocybin administration on which they will rate various dimensions of psychological set (e.g., the extent of pre-session apprehension, preoccupation with thoughts and problems not related to the session, positive expectation).

*Staff Rating of Likely Experience*: Study staff will complete a questionnaire before the session rating their expectations about the likely nature of the drug experience for that subject (e.g. likelihood that the experience will be interpreted as being spiritually significant or personally meaningful, or will involve a period of significant fear). This form was used in our previous psilocybin study (Griffiths et al., 2006).

# Measures taken throughout psilocybin session (10 min. before capsule, and 30, 60, 90, 120, 180, 240, 300 min. after capsule; psilocybin condition only):

*Within-session Monitor rating form:* At the same timepoints at which the heart rate and blood pressure will be taken, the two study staff will independently complete the Monitor Rating Form, which we used in our first psilocybin study. The form involves rating or scoring 26 dimensions of the subject's behavior and mood (e.g., yawning, minutes sleeping, minutes speaking, nausea/vomiting, motor activity, sedation, anxiety/fear, paranoia, crying, sorrow/sadness, joy/intense happiness, peace/harmony, overall drug effect).

*Heart rate and blood pressure:* At 10 minutes before and 30, 60, 90, 120, 180, 240, and 300 minutes after psilocybin administration, heart rate and blood pressure will be monitored for safety and because psilocybin is known to produce modest but reliable elevations in blood pressure (Griffiths et al., 2006; Gouzoulis-Mayfrank et al., 1999b; Hasler et al., 2004).

*Video and audio recordings:* Video and audio recordings, which will be taken throughout the psilocybin session, will be reviewed by investigators. Video and audio recordings will permit an objective assessment of session activity and will provide a rich source of additional data about subject comments and behavior during the session that may be useful in characterizing the effects of psilocybin. Video and audio recordings will be treated as confidential research materials and will be stored in locked offices.

#### Measures taken about 7 hours after psilocybin administration:

*Mystical Experience Questionnaire* (MEQ; MacLean et al., 2012): This 30 item scale is an abbreviated version of the 100 item States of Consciousness Questionnaire (Pahnke, 1969; Richards, 1975; Richards et al., 1977). The MEQ was derived via exploratory factor analysis, and is intended to characterize the impact of single hallucinogen-occasioned drug sessions for common elements of mystical experience (e.g., unity, sacredness, transcendence of time/space, ineffability).

*Hallucinogen Rating Scale* (Strassman et al. 1994; Riba et al. 2001): This questionnaire, which was designed to show sensitivity to the hallucinogen N,N-dimethyltryptamine, consists of six subscales assessing various aspects of hallucinogen effects (intensity, somaesthesia,, affect, perception, cognition, and volition). This scale was shown sensitive to the effects of psilocybin in our previous study (Griffiths et al., 2006).

*Post-session Monitor Rating Form*: On this form, which was used in our previous study of psilocybin (Griffiths et al., 2006), monitors will rate the qualitative nature of the session at the conclusion of each session.

#### Measure taken the day after psilocybin session (psilocybin condition only):

*Next-day Monitor Rating Form*: On this form, which was used in our previous study of psilocybin (Griffiths et al., 2006), study staff will rate the qualitative nature of the session the day after each session after meeting with the volunteer.

*Headache Interview Form:* This 14-item interview assesses incidence, duration, and severity of headache during or immediately after psilocybin sessions, as headaches have been found to occur in some individuals post-psilocybin (Johnson et al., 2012).

#### c. Statistical plan including sample size justification and interim data analysis.

This is a pilot comparative efficacy study with a randomized control condition. Demographics and smoking history at baseline will be examined for between group differences using Fisher's exact tests and independent-samples t-tests. The primary outcome variable will be a between group comparison of the percent of volunteers who show biologically verified (via carbon monoxide and cotinine measures) and self-reported smoking abstinence post-TQD, allowing for a grace period for initiation of prolonged abstinence within 14 days after the target-quit date in line with current recommendations for best practices in smoking cessation clinical trials (Piper et al., 2020). For this primary analysis, positive cotinine samples will be counted as smoking abstinent if the person indicates on the TLFB that they have used non-smoking forms of nicotine. This comparison will be performed using a logistic regression analysis, with treatment condition

as the predictor variable and prolonged abstinence as the examined outcome. Although the study sample will be small, these results will provide useful preliminary data indicating whether follow up investigation in this area is warranted. Between groups comparisons of secondary measures will examine differences across treatment conditions on variables such as smoking urges and withdrawal using independent-samples t-tests. We will apply a 2-step approach when assessing between-group differences in these variables. First, we will compare values between all participants still enrolled in the study at 6-months post-TQD, then only among those still smoking at 6 months post-TQD according to 7-day point prevalence criteria. In order to rule out the role of alternative sources of nicotine in achieving smoking abstinence, we will perform a secondary analysis where participants who stopped smoking tobacco cigarettes and initiated alternative forms of nicotine use (e.g., e-cigarettes, smokeless tobacco) will be coded as non-abstinent.

Neuroimaging data will be analyzed to account for differences in BOLD signal and functional connectivity related to task parameters between groups. Resting state MRI will be assessed between groups and within-subjects as a function of relapse status to examine whether characteristics of resting state functional connectivity (rsFC) are associated with treatment success (vs. failure). Additionally, behavioral performance on each of the fMRI tasks assessing working memory, attention, processing speed, inhibitory control processes, cognitive control, reward responsiveness, amygdala, striatal, and impulsive decision making (e.g., reaction time, error rate, hit rate, reward bias) will provide task-related parameters necessary for analysis of BOLD and resting state data. Self-reported craving, withdrawal symptoms and mood/affect will also be employed as regressors in the analysis of task and resting BOLD data. No interim data analyses are planned.

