In total, 115 participants will complete this pilot study. Fifteen individuals have already undergone the initially approved protocol with no clinically significant adverse events. A further 100 participants will be randomized to a psilocybin condition or a nicotine replacement therapy (NRT; i.e., transdermal nicotine patch) condition, 60 of whom will be studied with functional neuroimaging procedures. The NRT condition will serve as an important control for evaluating relative efficacy of the psilocybin condition, as well as examining differences in neuroimaging results. After screening and enrollment, individuals who are eligible for MRI scanning (n=60) will be invited to complete an optional preliminary sub-study protocol consisting of a 6-8 hour MRI scan, blood draw, and questionnaire assessment at the National Institute on Drug Abuse (NIDA) Intramural Research Program on the Johns Hopkins Bayview Campus. After completing the sub-study protocol, or opting out, participants will begin a 13-week cognitive-behavioral smoking cessation intervention, with Target Quit Date (TQD) set in approximately week 5. Participants who are eligible for and willing to participate in MRI scanning (n=60), will have MRI scans conducted in weeks 2 and 5, and at 3-month follow-up for those participants who have maintained smoking abstinence to that point. Individuals who do not meet MRI scanning inclusion criteria, but are otherwise eligible to enroll (n=40), will complete only the treatmentrelated portions of the study.

During the third treatment meeting in week 3, participants will be randomized into one of two treatment conditions (i.e., psilocybin or NRT). In one condition a single high-dose

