(30mg/70kg) of psilocybin will be administered in the context of a 13-week smoking cessation treatment protocol. In the other condition an 8 to 10 week regimen of NRT (patch) will be administered within the same 13-week treatment protocol. Participants in both conditions will meet weekly with study staff during weeks 1-7, and at two-week intervals during weeks 8-13 (i.e., in weeks 9, 11, and 13) of the 13-week treatment period. All participants will be asked to complete follow-up meetings at 3, 6, and 12 months post-TQD to assess smoking status and complete questionnaires. Additionally, in order to prevent differential dropout driven by individuals who hope to receive the novel psilocybin treatment, participants randomized to the NRT condition will be offered an optional psilocybin (30 mg/70 kg) session after completing their 6-month follow-up.

A number of measures that assess the psychological process of smoking cessation will be utilized at intake and repeatedly after the psilocybin session or initiation of NRT. In order to explore the contribution of spiritual experience to smoking cessation success in the psilocybin treatment condition, questionnaires that assess the spiritual nature of the psilocybin session experiences will be given after the psilocybin session. In order to assess the hypothesis that spiritual experience or smoking cessation is associated with changes in immune function or stress hormones, blood samples at baseline and 1-week post-TQD will be collected from both groups for cytokine and hormonal analyses when possible. Diurnal saliva samples of cortisol will also be assessed at baseline, and 1-week post-TQD. In order to examine neural mechanisms associated with psilocybin-facilitated smoking cessation, MRI data will be compared withinsubjects and between treatment groups in a subset of up to 60 participants who complete MRI scanning procedures.

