#### 3. Study Procedures

### a. Study design, including the sequence and timing of study procedures (distinguish research procedures from those that are part of routine care).

Study design: For this revised study protocol we will randomize 80 participants to complete a 13-week cognitive-behavioral therapy treatment protocol involving either a single high-dose (30mg/70kg) administration of psilocybin, or an 8 to 10 week course of NRT (transdermal nicotine patch) for smoking cessation. Participants will be nicotine-dependent cigarette smokers, who have had multiple unsuccessful quit attempts, and who continue to desire to quit smoking. Other than nicotine dependence, participants will be physically and psychologically healthy. In total, 95 participants will complete the study, including 15 individuals who have already completed psilocybin-facilitated treatment before the current protocol modifications, and 80 further individuals to be recruited for the revised study design including NRT control arm. Fifty participants will also undergo MRI data collection before and after treatment to inform neurobiological mechanisms of action. After screening and enrollment, participants will complete several baseline measures, and those who have consented to participate in the MRI scanning component will be invited to participate in an optional NIDA sub-study protocol. Participants will begin a 13-week cognitive-behavioral smoking cessation program consisting of weekly meetings with two trained study staff members for weeks 1-7 of study treatment, and meetings every other week thereafter (i.e., weeks 9, 11, and 13). For the revised study protocol up to 60 participants will undergo an MRI scan in week 2 of study treatment, and will be required to abstain from smoking for 24 hours before all MRI scans as verified by breath carbon monoxide measures. An additional 30 individuals who do not meet MRI scanning inclusion criteria (e.g., are left handed), but are otherwise eligible to enroll, will complete only the treatment-related portions of the study. During the third treatment meeting in week 3, participants will be randomized into one of two treatment conditions (i.e., psilocybin or NRT).

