After completing the 6-month follow-up, participants initially randomized to the NRT condition (n=40) will be given the option to undergo a single high-dose (30mg/70kg) psilocybin session. If they choose to take part, they will receive two weekly preparation meetings, one psilocybin session and next-day integration meeting, and two weekly follow-up meetings. For individuals still smoking at that time, the session will serve as an additional quit attempt and provide further data on psilocybin-facilitated smoking cessation. For participants who are no longer smoking, the session will focus on promoting long-term abstinence. The rationale for offering an optional psilocybin session to all participants in the NRT condition is twofold. Firstly, we hope to reduce differential dropout among participants randomized to the NRT condition, and encourage them to complete study treatment through 6-month follow-up. Secondly, in offering this optional session to those who were both successful and unsuccessful in quitting smoking using NRT, we can avoid encouraging poor treatment compliance in the NRT condition (i.e., intentionally failing to quit smoking in order to receive additional treatment with psilocybin). For participants from the NRT condition who choose to take part in the optional psilocybin session, the remaining long-term follow-up meeting will be shifted to take place at 6 months after their psilocybin session (in place of their original 12-month follow-up). For participants from the NRT condition who decline to take part in the optional psilocybin session, study follow-ups will proceed as originally planned at 12 months after their originally assigned Target-Quit Date.

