Volunteers who fail screening at BPRU but who, in the judgment of the investigators, might be eligible for a future study will be asked to complete IRB-approved HIPAA-IRB Form 3 "Authorization to contact you about future research studies." Volunteers' files will be kept in a locked room and treated as confidential research material. All data will be collected using the unique identification code numbers assigned to each volunteer upon entry to the study. No individual identifiable information will be released without written authorization. These procedures have been used in the past to protect confidentiality of study data and no instance of loss of confidential information has occurred.

Two hundred volunteers will sign consent to be screened to provide 130 participants who start the study, and 115 participants to participate until completion. Consent will be obtained at BPRU at a scheduled meeting after volunteers have passed telephone screening. Due to COVID-19 space restrictions, participants and study staff may review the consent form remotely or onsite in separate rooms over a secure online platform (e.g., Zoom) to go over study procedures and answer questions before signing consent. Informed consent will be signed at BPRU in-person. Participants will be provided an information sheet about COVID-19 per JH SOM Research Visit Guidelines, as well as information about personal protective equipment (PPE) requirements for their upcoming visit. Participants will be encouraged to socially distance per national and regional guidelines. Written informed consent will be updated to reflect the measures described herein.

Participants will complete a pre-visit COVID-19 symptom questionnaire within 24 hours of all in-person visits, and/or be screened with a symptom questionnaire upon arrival at the Behavioral Pharmacology Unit (BPRU). The screening questionnaire will assess for possible COVID-19 symptoms including:

- Elevated body temperature
- Presence of cough
- Loss of smell or taste
- Presence of fatigue or general malaise
- Presence of headache
- Presence of body aches
- Adherence to social distancing guidelines
- Known contact with an individual who tested positive for COVID-19 in the past 14 days

• Engagement in high-risk behaviors (e.g. participation in large gatherings without social distancing or use of PPE)

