 At baseline screening, at each treatment meeting, and at 3, 6, and	Toronto Alexithymia Scale 
12 month follow ups	• TCI Self-transcendence subscale 
*	• MAP (Measure of Actualization of Potential) 
 At baseline screening, week 2, week 5 of treatment, and 3-month	• Five Facet Mindfulness Questionnaire 
follow-up*	Schwartz Value Scale 
	• Purpose In Life Test (PIL) 
 At baseline screening, I week after IQD, 8 weeks after IQD,	• Delay / Health discounting & Elasticity of Demand 
and 6 month follow up	• Zimbardo Time Perspective Inventory (ZTPI) 
$^{11}$ At baseline screening 8 weeks after TOD 6 and 12 month	• Future Time Perspective (FTP) 
follow up	Visual Effects Questionnaire 
	
 
Hood Mysticism Scale (lifetime) 
 

 At baseline screening, at TQD, at 1 through 8 weeks after TQD,	• Blood markers: Cortisol, ACTH, IL-4, IL-6, IL-10,
3, 6, and 12 month follow up	INF-gamma, TNF-alpha, Gs-alpha 
	• Persisting Effects °
 At baseline screening, 1 week after TQD, and 6 month follow	• States of Consciousness Retrospective Questionnaire
up	• Adverse Events form
14 At herealing spreaning 6 and 12 month full	• Open-ended clinical Interview '
At basenne screening, 0, and 12 month follow ups	
 
Information Rating of Enduring Effects '
 
Saliva samples for cortise15
 

 At baseline screening, 2 weeks after TOD and 6 month follow	• Sanva samples for corusol
up	• Functional Neuroimaging: MKI scanning 
 At baseline screening, 4 weeks after TQD	

<sup>† MRI scanning procedures will occur only for those individuals who are deemed MRI eligible and consent to do so (n=60). \*3-month follow-up MRI Scan 3 only for MRI participating volunteers showing biologically verified 7-day point-prevalent abstinence at that time.

*Zimbardo Time Perspective Inventory* (ZTPI): This validated questionnaire assess the construction of psychological time, and includes 56 questions scored on a 5-point scale with subscales assessing past negative, present hedonistic, future, past positive, and present fatalistic dimensions (Zimbardo & Boyd, 1999).

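### The step 1 secondary comparison uses only people still enrolled at 6 months and discards leavers' earlier values, so the arm difference may be biased if reasons for leaving differ by arm

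*Combined protocol and SAP*

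**What the plan says.** Section 6c (Statistical plan) compares the arms on "variables such as smoking urges and withdrawal using independent-samples t-tests". It then sets a two-step rule. Step 1 reads: "First, we will compare values between all participants still enrolled in the study at 6-months post-TQD". Step 2 narrows to those still smoking and is not at issue here. Section 6c gives no method for missing secondary data.

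The outcome table in Section 6b shows what exists for someone who leaves early. The smoking urges and abstinence self-efficacy questionnaires follow this schedule: "At baseline screening, at each treatment meeting, and at 3, 6, and" 12 months. The withdrawal scale is listed at baseline, at the target quit date (TQD), in weeks 1 to 8 after it, and at 3, 6 and 12 months. The BSI, BDI, STAI and PANAS-X are listed at baseline, 8 weeks, and 3, 6 and 12 months.

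On dropout, the Abstract says that NRT participants are offered a psilocybin session after the 6-month visit "in order to prevent differential dropout driven by individuals who hope to receive the novel psilocybin treatment". Section 3a repeats the reason: "we hope to reduce differential dropout among participants randomized to the NRT condition". Section 3c states that the trial is not blinded. The only attrition figure, in Section 3a, is "130 participants who start the study, and 115 participants to participate until completion". It is not split by arm.

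**The concern.** Randomisation balances the arms among everyone randomised. It does not balance them among those who remain 6 months later. If, for example, NRT participants with strong urges leave more often than comparable psilocybin participants, the remaining NRT group looks better than the full group would, and a psilocybin advantage shrinks. If leaving runs the other way, the advantage is inflated. Participants know their arm when they decide whether to stay, and removal for non-compliance (Section 3f) is a second way out.

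The restriction also throws away information that bears on the problem. A leaver's urge score at 3 months says something about the missing 6-month score, and step 1 does not use it. Section 2 says these measures may help in designing later controlled trials, so a distorted craving or withdrawal effect could be carried into that planning.

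**Working it through.** **Attrition in the plan.** 130 start and 115 complete: 1 − 115/130 = 11.5%. If the 15 people treated under the earlier protocol are in both counts (an assumption), 1 − 100/115 = 13.0%. No rate by arm, effect size, SD or power calculation is stated, so there is no planned figure to reproduce for the secondary measures.

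**Sample size.** The Abstract says "A further 100 participants will be randomized to a psilocybin condition or a nicotine replacement therapy"; Section 3a says "we will randomize 80 participants to complete a 13-week cognitive-behavioral therapy treatment protocol". These must be reconciled. I use 50 per arm. The choice changes the standard error but hardly the bias.

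**Standard error of step 1 in SD units.** With 13% lost per arm, 50 × 0.87 = 43.5 remain, so SE = √(1/43.5 + 1/43.5) = 0.21. With 40 per arm, 34.8 remain and SE = 0.24.

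**Simulation under no true difference.** The assumptions are SD 1; correlation ρ between the 3- and 6-month values of 0.5 or 0.7; probability of leaving logistic in the 3-month value with slope ±1 per SD (0 where unrelated); 6,000 runs. Bias is psilocybin minus NRT. Higher scores mean stronger urges, so a positive bias works against psilocybin. Every scenario averages 13% dropout.

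| Dropout, psilocybin / NRT | Who leaves | Bias, ρ 0.5 / 0.7 | Type I error (nominal 5%) |
|---|---|---|---|
| 13% / 13% | high urge, both arms | 0.00 / 0.00 | 5.1% / 4.8% |
| 5% / 21% | unrelated to outcome | about 0 / about 0 | 5.0% / 5.4% |
| 8% / 18% | high urge, both arms | +0.04 / +0.06 | 5.7% / 5.7% |
| 5% / 21% | high urge, both arms | +0.06 / +0.10 | 6.2% / 7.1% |
| 5% / 21% | low urge, both arms | −0.07 / −0.10 | 6.3% / 6.5% |
| 13% / 13% | high urge on psilocybin, low urge on NRT | −0.11 / −0.16 | 8.8% / 11.7% |

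Unequal rates alone do not produce bias (row 2), and equal rates do not rule it out (row 6). What matters is why people leave.

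**With a true difference of −0.40 SD.** Dropout is 10% on psilocybin and 15% on NRT, averaging 12.5%. If leaving is random on psilocybin and craving-driven on NRT, step 1 returns −0.335 / −0.312: (0.40 − 0.335)/0.40 = 16% and (0.40 − 0.312)/0.40 = 22% too small. With the same craving mechanism in both arms it returns −0.380 / −0.372, which is 5% and 7% too small.

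**Limiting case.** If exactly the highest-urge fraction q leaves, the mean among those who stay shifts by −ρ·φ(c)/(1 − q), with c = Φ⁻¹(1 − q). For q = 0.21 this is −0.7 × 0.288/0.79 = −0.255; for q = 0.05 it is −0.7 × 0.103/0.95 = −0.076. The bias at ρ = 0.7 is −0.076 + 0.255 = +0.18 SD. Putting all attrition on NRT (0% against 26%) gives +0.31 SD. Only that boundary case exceeds one standard error.

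**Using the earlier values.** Regressing the 6-month on the 3-month value within each arm and averaging over everyone randomised brings the bias to within about 0.01 SD of zero in every simulated scenario, with an almost identical standard error. This is partly by construction: leaving depended on a 3-month value that every leaver had supplied. When leavers' 3-month values are removed in the −0.40 case, the estimator returns −0.332 / −0.303, no better than step 1.

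**The case against.** The protocol does not leave the risk alone. The delayed psilocybin session is a deliberate retention measure. It is open to NRT participants who are still smoking, which may keep in exactly the high-craving people whose loss would matter. Stopping the patch is not leaving: such participants are asked to complete the study meetings, and Section 7b continues data collection after adverse effects. Being still enrolled is therefore broader than having completed treatment. The dropout that the protocol describes comes from disappointment at allocation. Some of these people could leave between randomisation in week 3 and the TQD in about week 5, before any post-quit value exists, and a repeated-measures model recovers little for them. A model using every scheduled withdrawal assessment would also be unwieldy: TQD, weeks 1 to 8, 3 and 6 months make 11 visits and 11 × 12/2 = 66 covariance parameters for 80 to 100 people.

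All of this stands, and it limits the size of the problem and the reach of the remedy. It does not supply a reason to ignore the values that leavers did give.

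A reader might go further and infer that the protocol expects dropout to differ by arm and that step 1 is therefore biased. The text does not say so: it names a risk and a measure meant to prevent or reduce it. A reader might also infer that a real effect could be roughly halved. With a true −0.40 SD, 35% craving-driven dropout on NRT and 10% random dropout on psilocybin do give −0.196 (51% too small) at ρ = 0.7. But that is 22.5% overall, well above the planned 11.5 to 13%.

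**Conclusion.** The point holds as a possible bias in the secondary comparisons. Step 1 is a completer analysis by explicit rule, it discards repeated measurements that the protocol schedules, and nothing in Section 6c guards against informative dropout. Near the planned attrition, the bias in the simulated scenarios runs from about zero (same mechanism and rate in both arms, or leaving unrelated to outcome) to about 0.1 to 0.16 SD (mechanisms that differ by arm). That is below one standard error of about 0.21 SD. These sizes rest on the assumed correlations, dropout splits and logistic mechanism, none of which the documents give, and the direction is open.

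The sentence does not name the visit whose values are compared. Whether it means the 6-month values or values from all visits, leavers are excluded. The primary abstinence comparison is outside this rule. For secondary measures in a pilot study this is a worthwhile, inexpensive improvement and not a fatal flaw.

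**What to change.** For secondary measures with repeated post-TQD assessments, make the main analysis a likelihood-based repeated-measures model on all randomised participants:

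- Keep baseline in the outcome vector with a common mean across arms (constrained baseline), so that people who leave before any post-TQD value still contribute.
- Prespecify a small visit set, for example 1 week where collected, 8 weeks, 3 and 6 months. With baseline that is five occasions and 5 × 6/2 = 15 covariance parameters.
- Include arm-by-visit terms and an unstructured covariance, and state a fallback structure in case the model does not converge.
- Name the 6-month arm difference as the estimate.
- Keep the planned t-test among those still enrolled as a sensitivity analysis.
- Report dropout and its reasons by arm, and add a missing-not-at-random sensitivity analysis, such as shifting leavers' unobserved values by arm.

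The cost is revised wording in Section 6c and some programming. No new visits, data or participants are needed, and the simulations showed no loss of precision. The limits should be stated: the model assumes missing at random given the observed values, recovers little for people who leave before the TQD, and does not help measures with no post-TQD value before 6 months, such as the Hood Mysticism Scale.

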#### f. Definition of treatment failure or participant removal criteria.

Treatment failure is defined by the inability to achieve 7-day point-prevalence abstinence at 6month follow-up, as confirmed by urine cotinine, breath carbon monoxide, and self-report data. However, all participants will be evaluated throughout the initial 12-month follow up regardless

if they have quit smoking. Participants will be removed from the study for non-compliance with study requirements.

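### The second-step t-test of secondary measures, restricted to people still smoking at 6 months, is not a randomised comparison and can mislead in either direction; baseline values are collected but not used

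*Combined protocol and SAP*

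**What the plan says.** All references are to the combined protocol and SAP.

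- **Test.** Section 6c compares the arms "on variables such as smoking urges and withdrawal using independent-samples t-tests". It names no covariate for these tests. The regressors mentioned later in that section concern imaging data only.
- **Populations.** The tests are run in two steps: "compare values between all participants still enrolled in the study at 6-months post-TQD, then only among those still smoking at 6 months". Step 2 identifies smokers by 7-day point prevalence. The plan does not call step 2 descriptive and does not say what it estimates.
- **Status of the step 2 filter.** Section 3f uses the same criterion at the same time for failure: "Treatment failure is defined by the inability to achieve 7-day point-prevalence abstinence at 6month follow-up". It is related to the primary outcome but not identical. The primary logistic regression takes treatment condition "as the predictor variable and prolonged abstinence as the examined outcome", with a 14-day grace period.
- **Data available.** The table of measures in section 6b schedules the urges questionnaire (QSU) and the withdrawal scale (WSWS) at baseline, repeatedly during treatment, and at 3, 6 and 12 months. Section 3f adds that "all participants will be evaluated throughout the initial 12-month follow up regardless" of whether they have quit.
- **Dropout.** Section 3a plans for "130 participants who start the study, and 115 participants to participate until completion", with no split by arm. The optional later psilocybin session for the NRT arm is offered "in order to prevent differential dropout driven by individuals who hope to receive the novel psilocybin treatment" (section 1); section 3a says similarly "we hope to reduce differential dropout among participants randomized to the NRT condition".

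**The concern.** Randomisation makes the arms comparable as assigned. It does not make comparable those who remain smokers six months later, because treatment may change both how many people quit and which people quit. A difference in urges or withdrawal between the two groups of remaining smokers therefore mixes any effect of treatment with a difference in who is left. The plan nevertheless gives this comparison the same t-test as step 1.

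The unadjusted test is a separate, lesser matter. It is valid, but it gives up precision that the scheduled baseline values would supply at no extra data cost.

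The stakes lie in the secondary objective (section 2). These measures are meant to show which factors matter to the intervention and to help design later trials. A step 2 result could point that work the wrong way.

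**Working it through.** The plan states no effect size, SD, alpha, expected abstinence or power for these comparisons, so there is no figure to reproduce. Inputs from the documents: 80 randomised, 40 per arm (section 3a), or 100 randomised (section 1; 50 per arm assumed). Everything else is assumed: two-sided alpha 0.05, a measure with SD 1 on which higher is worse, and the abstinence rates and correlations below. Differences are psilocybin minus NRT, so a positive value counts against psilocybin.

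**1. Bias of step 2 with no treatment effect on the measure.** Let a latent propensity to quit have correlation -r with the measure, and let a person quit if it exceeds c = z(1 - quit rate). The mean among remaining smokers is r × m, where m = φ(c)/Φ(c).

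- Quit rate 50%: c = 0, m = 0.3989/0.50 = 0.798
- Quit rate 25%: c = 0.674, m = 0.3178/0.75 = 0.424
- Quit rate 35%: c = 0.385, m = 0.3704/0.65 = 0.570

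Bias = r(psilocybin) × m(psilocybin) - r(NRT) × m(NRT):

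| Abstinence, psilocybin v NRT | r, psilocybin / NRT | Bias (SD) |
|---|---|---|
| 50% v 25% | 0.1 / 0.1 | 0.1 × (0.798 - 0.424) = +0.04 |
| 50% v 25% | 0.3 / 0.3 | 0.3 × 0.374 = +0.11 |
| 50% v 25% | 0.7 / 0.7 | 0.7 × 0.374 = +0.26 |
| 50% v 25% | 0.1 / 0.5 | 0.080 - 0.212 = -0.13 |
| 35% v 35% | equal | 0.00 |
| 35% v 35% | 0.1 / 0.5 | 0.057 - 0.285 = -0.23 |
| 35% v 35% | 0.5 / 0.1 | 0.285 - 0.057 = +0.23 |

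At 40% v 30% with equal r of 0.1 to 0.7, the bias is only +0.01 to +0.10 SD. By simulation, the false-positive rate at 50% v 25% with r = 0.7 in both arms is about 17% (40 per arm) or 21% (50 per arm). At 35% v 35% with r 0.1 / 0.5 it is about 13% or 15%.

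**2. A second model, as a check on direction.** A dependence trait drives both quitting and the score (loading 0.6), and smoking adds 0.5 SD to the score. At 50% v 25%, a true direct benefit of -0.50 SD appears in step 2 as:

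- -0.37 SD if less dependent people quit in both arms;
- -0.50 SD if quitting is unrelated to dependence;
- -0.65 SD if only NRT quitting is selective;
- -0.86 SD if psilocybin mainly helps the more dependent to quit.

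A real benefit can thus be shrunk, left alone or exaggerated.

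**3. Does baseline adjustment repair step 2?** No. With baseline correlation 0.6, ANCOVA among remaining smokers at 50% v 25% and equal r of 0.1 to 0.7 still has a bias of 0.02 to 0.19 SD.

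**4. What step 2 could detect.** At 50% v 25%, the remaining smokers number 40 × 0.50 = 20 v 40 × 0.75 = 30, or 25 v 37.5 with 50 per arm. A two-sample t-test then has 80% power only for 0.83 or 0.74 SD.

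**5. Gain from the baseline value in the whole sample.** Without dropout the standard error falls by 1 - √(1 - ρ²): about 5%, 13%, 20% and 29% at ρ = 0.3, 0.5, 0.6 and 0.7. For a 0.50 SD effect at ρ = 0.5, power rises from 60.9% to 73.3% (40 per arm) or from 70.5% to 82.3% (50 per arm).

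**6. Step 1.** It is not selected on smoking status. It excludes leavers, and is biased only if dropout between randomisation and month 6 differs by arm in amount or kind and is related to the measure. The planned loss, (130 - 115)/130 = 11.5%, runs from study start to completion. Randomisation is in week 3 and follow-up lasts to month 12, so this is not the dropout relevant here. The documents give no figure for that, and no bias is computed for step 1.

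**The case against.** The strongest reply is that step 1 comes first and compares smokers and abstainers together. A real reduction in urges should show there, and nothing says that step 2 overrides it. An unadjusted t-test is valid, the offer of a later psilocybin session already addresses differential dropout, and these are secondary measures in a declared pilot. All of that stands. It limits the harm, but it does not give step 2 a meaning that would justify a test.

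Three stronger readings are tempting, and the documents support none of them:

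- **That step 2 would mainly mask a benefit.** This needs more quitting under psilocybin and the same kind of person quitting in both arms. The documents establish neither, and the treatments differ enough in kind (section 3c) that different selection is plausible. Other patterns create or inflate a benefit.
- **That equal abstinence makes step 2 safe.** This holds only if selection is also alike. Unequal selection gives a bias of 0.23 SD in either direction at 35% v 35%.
- **That step 1 is materially biased by the planned attrition.** The 11.5% covers the wrong interval and has no split by arm.

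**Conclusion.** The point holds for step 2 as a matter of design: it tests a subset defined by an outcome after randomisation, and the result can hide, create or exaggerate a difference. The size is not known. Under the assumed inputs of the first model it runs from -0.23 to +0.26 SD, and it is zero when abstinence and selection are both alike or when the measure is unrelated to quitting. Observed abstinence rates alone cannot show which case applies. The missing baseline adjustment is a loss of precision, not a source of bias. Step 1 is free of the step 2 selection but is not a comparison of everyone randomised. The primary analysis is unaffected. Severity: minor to should-fix.

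**What to change.** Replace the two-step description in section 6c with:

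(a) For each secondary measure with a baseline value, estimate the 6-month difference between assigned arms, smokers and abstainers together, adjusted for the baseline value (ANCOVA), with a 95% CI.

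(b) Report participants still smoking at 6 months by arm (n, mean, SD), with no between-arm p-value and no causal interpretation.

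Optionally, for QSU and WSWS, add a repeated-measures mixed model (baseline, arm, visit, arm by visit) and state its assumption that dropout is explained by observed values. Its purpose is to keep the earlier data of people who leave after giving a value following the target quit date. It does not recover those who leave before that date.

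The cost is wording, slightly more analysis and, if the mixed model is used, one stated missing-data assumption. No new assessments are needed. The study gives up a formal test in a small, non-randomised subset.
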